11.2. Access to data, handling of data and samples (data protection), archiving (p	
11.3. Data entered directly in the Case Report Form (CRF) – definition of source data	34
11.4. Data and safety monitoring board (WHO) / data monitoring committee (EU/FDA)	35
11.5. Study Documents: Translations - Reference language	35
12. Dissemination of results and publication	35
13. References	36

IV. Abbreviations

AE Adverse event

AUC Area under the curve
CI Confidence interval

CR Cure rate

CRF Case report form

DALYs Disability-adjusted life years

DBS Dried blood spot

DSMB Data and safety monitoring board

EKNZ Ethikkomission Nordwest- und Zentralschweiz

EPG Eggs per gram

ERR Egg reduction rate

GCP Good clinical practice

Hb Hemoglobin

ICH International council for harmonisation of technical requirements for

pharmaceuticals for human use

IEC Independent ethics committee

LC-MS/MS Liquid chromatography tandem mass spectrometry

MIC Minimal inhibitory concentration

NLME Nonlinear mixed-effects
PI Principal investigator

PK Pharmacokinetic

PKPD Pharmacometric-pharmacodynamic

SAE Serious adverse event
STH Soil-transmitted helminth
WHO World Health Organization

V. Synopsis

Study Title	Efficacy and safety of ascending dosages of albendazole against T. trichiura and hookworm in preschool- and school-aged children and adults: a randomized controlled trial			
Short title	Albendazole dose finding and pharmacokinetics in children and adults			
Study Type	Phase 2 trial			
Sample size	1040			
Indication	T. trichiura and hookworm infection (eggs in stool)			
Investigational Product and Reference Treatment	Albendazole			
Protocol Number, Date and Version	1, 25.02.2018, v1.01			
Trial registration	ClinicalTrials.gov: NCT03527745			
Study Rationale	To determine the range of doses of albendazole against infection with T. trichiura and hookworm which are effective and tolerated by preschool-aged children, school-aged children and adults.			
Study Objectives	To determine the efficacy and safety of ascending oral albendazole dosages in children and adults infected with T. trichiura and in children and adults infected with hookworm. In preschool-aged children: (i) 200 mg, (ii) 400 mg and (iii) 600 mg; and in schoolchildren and adults: (i) 200 mg (only for hookworm infections), (ii) 400 mg, (iii) 600 mg and (iv) 800 mg will be compared against both parasites (T. trichiura and hookworm). Additionally, albendazole disposition will be measured in children and adults using a microsampling device.			
	Our primary objective is to determine the dose-response base on cure rates of albendazole in (i) preschool-aged children (2-years), (ii) school-aged children (6-12 years) and (iii) adults (≥ 2 years) infected with T. trichiura and in (i) preschool-aged children (2-5 years), (ii) school-aged children (6-12 years) and (iii) adult (≥ 21 years) infected with hookworm.			
	The secondary objectives of the trial are:			
	a) To determine the efficacy based on egg reduction			
L	Page 8 of 36			

	rates of albendazole in preschool-aged children, school-aged children and adults; b) To determine an exposure (including Cmax, AUC and tmax)-response correlation of albendazole in preschoolaged (2-5 years), school-aged children (6-12 years), and adults (≥ 21 years); c) To evaluate the safety and tolerability of albendazole in preschool-aged children, school-aged children and adults; and d) To determine the efficacy against concomitant soil-transmitted helminthiasis (Ascaris lumbricoides) e) To assess genetic heterogeneity in hookworm and T. trichiura populations with regard to the efficacy of different doses of albendazole.		
Study design	Single blind, randomized controlled trial (participants and lab technicians are blinded)		
Study product / intervention	Administration of a single oral dose of albendazole		
Comparator(s)	Matching placebo (purchased from Fagron)		
Key inclusion / Exclusion criteria	Inclusion: preschool-aged children (2-5 years), school-aged children (6-12 years) and adults (≥21 years) infected with T. trichiura or hookworm, absence of major systemic illnesses, written informed consent signed by parents and/or caregivers for minors; and oral assent by school-aged children. Exclusion: Any abnormal medical conditions or chronic disease, negative diagnostic result for T. trichiura and hookworm, pregnancy, no written informed consent.		
Primary Endpoints	CR on T. trichiura and hookworm		
Secondary Endpoints	ERR against T. trichiura and hookworm and safety, pharmacokinetic parameters, genetic heterogeneity in hookworm and T. trichiura populations		
Exploratory Endpoints	None		
Interim Analyses	None		
Study Duration	6 months		
Schedule	08/2018 of first-participant in (planned) 04/2019 of last-participant out (planned)		
Measurements & procedures	At baseline, two stool samples will be collected, if possible, on two consecutive days or otherwise within a maximum of 5 days. The medical history of the participants will be assessed with a		

standardized questionnaire (for preschool-aged children this will be administered to the caregiver of the child). In addition a clinical examination will be performed by the study physician and venipuncture to examine biochemical parameters in the blood will be carried out by study nurses before treatment. Adults, children and caregivers of preschool-aged children will also be interviewed before treatment, 3 and 24 hours after treatment, and at follow-up (2-3 weeks after treatment) about the occurrence of adverse events. The efficacy of the treatment will be determined 14-21 days post-treatment by collecting another two stool samples. All stool samples will be examined with duplicate Kato-Katz thick smears. A subsample of children and adults will be sampled using finger pricking for micro-blood sampling at 0, 1, 2, 3, 4, 6, 8, 24 hours post-dosing to evaluate pharmacokinetic parameters. **Statistical Analyses** An available case analysis (full analysis set according to the intention to treat principle) will be performed, including all subjects with primary endpoint data. Supplementary, a per-protocol analysis will be conducted. CRs will be calculated as the percentage of egg-positive subjects at baseline who become eggnegative after treatment. Geometric mean egg counts will be calculated for the different treatment arms before and after treatment to assess the corresponding ERRs Bootstrap resampling method with 5,000 replicates will be used to calculate 95% confidence intervals (CIs) for ERRs. E_{max} models using the DoseFinding package of the statistical software environment R will be implemented to predict the dose-response curves in terms of CRs and ERRs. Noncompartmental and nonlinear mixed-effects (NLME) modeling will be used to determine PK parameters. **GCP** statement This study will be conducted in compliance with the protocol, the current version of the Declaration of Helsinki, ICH-GCP E6 (R2) guidelines as well as all national legal and regulatory requirements. **Key explanation for the** This study will be carried out in children, since an infection with T. inclusion of children trichiura and hookworm occurs most often in children and they are the main targets of preventive chemotherapy programs. Moreover, the exact dosage of albendazole in preschool and school-aged children has not yet been determined. Recruitment procedure Participants will be recruited from rural communities situated in Côte d'Ivoire and identified to have at least a moderate infection risk (prevalence: 10-49%) of *T. trichiura* or hookworm.

Coverage of damages	Winterthur Police Nr. 4746321, BERACA Côte d'Ivoire, No: to be issued
_	After the study has been completed all samples will be destroyed and case report forms will be kept for a minimum of 15 years (chapter 10).
	We declare no conflict of interest in relation to the investigated drugs.

2. Background information

Parasitic worm diseases such as infection with soil-transmitted helminths (STHs) that include infection with *Ascaris lumbricoides*, *Trichuris trichiura*, and hookworm still affect hundreds of millions of people mostly in the tropics and subtropics [1]. In terms of morbidity, they contribute to an estimated 3.3 million disability-adjusted life years (DALYs) lost globally according to recent estimates [2]. The symptoms of STH infections are non-specific and may only be apparent in heavily infected individuals. Infection is typically most intense and debilitating in children. Chronically infected children might suffer from malnutrition, physical and cognitive retardation, and reduced work performance in older age [3].

For disease control, preventive chemotherapy represents the cornerstone and is advocated by the World Health Organization (WHO) as a strategy with a rapid impact on morbidity control and easily implementable at a large scale by trained personnel outside the health sector (e.g. teachers) [4]. Currently there are five drugs on the WHO model list of essential drugs against STH infections and these drugs have been widely and effectively used [4, 5]. Among these five, albendazole and mebendazole, which belong to the benzimidazoles, are considered as treatment of choice against *A. lumbricoides*, *T. trichiura* and hookworm infections [4]. However, both drugs show only limited efficacy against *T. trichiura* infection (cure rates of 30% and 42%, respectively) [5] and only albendazole is moderately efficacious against hookworm when used as single oral doses.

To determine the dose-response of oral albendazole dosages: i) 200 mg, ii) 400 mg and iii) 600 mg versus iv) placebo in preschool-aged children and i) 400 mg, ii) 600 mg and iii) 800 mg versus v) placebo in school-aged children and adults infected with *T. trichiura* and i) 200 mg, ii) 400 mg and iii) 600 mg versus iv) placebo in preschool-aged children and i) 200 mg ii) 400 mg, iii) 600 mg and iv) 800 mg versus v) placebo in school-aged children and adults infected with hookworm.

The secondary study objectives are:

- 1.) To determine the efficacy based on egg reduction rates of albendazole in preschool-aged children, school-aged children and adults;
- To measure albendazole disposition using a microsampling technology (DBS or Mitra®) to determine an exposure (including Cmax, AUC and tmax)-response correlation of albendazole in preschool-aged (2-5 years), school-aged children (6-12 years) and adults (≥ 21 years);
- 3.) To evaluate the safety and tolerability of albendazole in preschool-aged children, school-aged children and adults;
- 4.) To determine the efficacy against concomitant soil-transmitted helminthiasis (*Ascaris lumbricoides*); and
- 5.) To assess genetic heterogeneity in hookworm and *T. trichiura* populations with regard to the efficacy of different doses of albendazole.

4. Methodology

4.1. Primary and secondary endpoint

Cure rate (CR) (primary endpoint, i.e. conversion from being egg positive pre-treatment to egg negative post-treatment) and egg reduction rate (ERR) (secondary endpoint). In addition, key pharmacokinetic parameters will be determined and safety of treatment evaluated (secondary endpoints).

4.2. Type of trial

Single blind, randomized controlled trial

4.3. Trial design

4.3.1. Baseline survey

Stool samples collection

Two stool samples will be collected from each participant until a total of 560 hookworm-infected participants (160 preschool-aged children, 200 school-aged children and 200 adults) and 480 *T. trichiura* infected participants (160 preschool-aged children, 160 school-aged children and 160 adults) are identified.

[figure not shown]
The Kato-Katz technique will be used for the quantitative assessment of STH infections. Two stool samples will be collected from each participant before treatment and from each sample duplicate Kato-Katz thick smears (41.7 mg each) will be prepared [8]. The slides will be analyzed under a microscope by experienced technicians and a subsequent independent quality control of sample results (approximately 10%) will be conducted. Results are considered correct if the following tolerance margin is not exceeded: (i) No difference in presence/absence of hookworm, A. lumbricoides and T. trichiura, (ii) egg counts are +/-10 eggs for counts ≤100 eggs or +/-20% for counts >100 eggs (for each species separately) [9]. In case discrepancies above the tolerance margin are noted in one or more slides, all slides are re-read by the local technicians. The new results are discussed, so that in case of discordant results, slides can be re-evaluated to reach consensus. Infection intensity expressed as the arithmetic and geometric mean egg counts per gram of stool (EPG) will be calculated for each treatment arm. All microscopically analyzed quadruplicate Kato-Katz thick smears will be destroyed within one day (after passing the quality control). Since drug efficacy could be influenced by genetic aspects, ~2 g of stool sample from each participant will be preserved in ethanol for further genetic analyses of hookworm and T. trichiura in Côte d'Ivoire and Switzerland.

[figure not shown]
Clinical examination and biological exams

At baseline, the medical history of *T. trichiura* and hookworm-infected participants in the study will be assessed with a clinical and physical examination carried out by the study clinician, who will assess weight, height, body temperature, pulse rate and blood pressure. Rapid diagnostic tests for malaria will be done to assess the presence of a *Plasmodium* spp. co-infection. Hemoglobin (Hb) levels will be detected using HemoCue to exclude severely anemic participants (below 80 g/l and 70 g/l Hb in school-aged and preschool-aged children,

respectively, according to WHO). Female participants above 10 years will be asked to produce a urine sample for pregnancy testing. Vital organ (kidney, liver etc.) functions will be evaluated before treatment and between 14 and 21 days after treatment through a biochemical assessment of 4 ml of venous blood. We will assess urea, creatinine, bilirubin, azotemia, Alanine Amino Transferase (ALAT), Aspartate Amino Transferase (ASAT) and blood cell counts (hematocrit, erythrocyte, platelets).

The six study cohorts (adults and school-aged children are summarized in one flow chart because the treatment schedule is identical) are presented in the figure below:

4.3.2. Assessment of efficacy after treatment

The efficacy of the treatment will be determined 14-21 days post-treatment by collecting another two stool samples which will be microscopically examined for *T. trichiura* and hookworm and for co-infections (*A. lumbricoides*) using duplicate Kato-Katz thick smears.

Participants will be considered *T. trichiura* and hookworm cured if no eggs have been found in the stool. EPG will be assessed by adding up the egg counts from the quadruplicate Kato-Katz thick smears and multiplying this number by a factor of six. Geometric and arithmetic mean egg counts will be calculated for the different treatment arms before and after treatment to assess the corresponding ERRs.

At the end of the study, all participants remaining positive for *T. trichiura* or hookworm will be treated with 400 mg albendazole, the current standard treatment.

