4.4. Measure to minimize bias

Study participants eligible for treatment will be randomly assigned to one of the treatment arms using a computer-generated, stratified block randomization code. The random allocation sequence with varying random blocks of 4 and 8 (or 5 and 10, respectively) stratified by 2 levels of baseline infection intensity (light and moderate *T. trichiura* and hookworm infections) will be provided by a statistician. Study-site investigators will be aware

of the study group assignment, whereas participants and laboratory technicians will be blinded.

Placebo controlled trials reduce the risk of potential bias that can also interfere with the observed outcomes. In previous studies (e.g. Coulibaly et al. 2017 Lancet Global Health), we have observed moderate cure and egg reduction rates in placebo treated children likely due to the low sensitivity of anthelminthic diagnostics. Children treated with placebo will be treated at follow up (3-weeks post treatment) with 400 mg albendazole. This treatment delay does not cause any harm.

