5.3. Exclusion criteria

- 1. Presence of acute or uncontrolled systemic illnesses (e.g. severe anemia, infection, clinical malaria) as assessed by a medical doctor, upon initial clinical assessment and liver function tests.
- 2. Known or reported history of chronic illness such as HIV, acute or chronic hepatitis, cancer, diabetes, chronic heart disease or renal disease.
- 3. Prior treatment with anthelmintics (eg, diethylcarbamazine [DEC], suramin, ivermectin, mebendazole or albendazole) within 4 weeks before planned test article administration.
- Received any investigational drugs or investigational devices within 4 weeks before administration of test article that may confound safety and/or efficacy assessments.
- 5. Known or suspected allergy to benzimidazoles.
- 6. Pregnant (urine testing) or breastfeeding women.

Participants who were diagnosed with a STH infection, but who were excluded from the study due to one or several of the above-mentioned exclusion criteria, including withdrawals will be offered standard anthelminthic treatment (albendazole). Children suffering from

clinical malaria (fever plus positive diagnostic test) will be treated according to national guidelines but will not be included in the trial.

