10.2. Evaluation of the risk-benefit ratio

Albendazole is a well-known, widely used drug in mass treatment programs against filariasis, and has little and mainly mild adverse events (headache, abdominal pain etc.). All community members enrolled in the study will benefit from a clinical examination and treatment against STHs. All participating subjects remaining positive for *T. trichuria*, hookworm and concomitant STH will be treated with albendazole (according to WHO recommendations).

Biological sampling (stool, blood) is always associated with potential risk of disease transmission. For this reason, only qualified persons with expertise will be involved in sample collection. They will only use sterilized material. Note that, painful swelling and/or numbness of the arm may occasionally occur as a result of blood sampling. These effects are usually transient. This procedure can also occasionally trigger reactions such as mild discomfort and weakness. These reactions are usually benign, short-lived and limited to feelings of weakness, accompanied by sweating. However, biological tests suggested in this work will provide important data on the health of the participants.

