10.6. Other aspects

We will include one arm of each study cohort treated with placebo. However, this group will be treated with a standard treatment of 400 mg single dose albendazole at the end of the study (3-4 weeks later); hence, this does not cause any medical concern. Patients generally are treated only in yearly intervals to reduce morbidity from chronic infections. A treatment delay of 3-4 weeks is not expected to cause any harm.

11. Quality control and quality assurance

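### No repeat pregnancy test is described before the end-of-study albendazole dose, which is the first active trial dose for placebo-arm women

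*Combined protocol and SAP*

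**What the plan says.** Section 5.3 lists as an exclusion "Pregnant (urine testing) or breastfeeding women". The test itself is described in section 4.3.1, in the paragraph on baseline clinical and biological examinations: "Female participants above 10 years will be asked to produce a urine sample for pregnancy testing". The next sentence of that paragraph deals with organ function, and there a repeat is specified: "functions will be evaluated before treatment and between 14 and 21 days after treatment". The schedule in section 4.6 marks stool diagnosis, biochemistry and adverse-event capture at follow-up. It has no row for a pregnancy test at any visit.

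Albendazole is given again, or for the first time, at the end of the study. Four places cover this:

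- Section 4.3.2: "At the end of the study, all participants remaining positive for" *T. trichiura* or hookworm are to receive 400 mg.
- Section 10.2: "All participating subjects remaining positive for" those parasites or a concomitant soil-transmitted helminth are to receive albendazole, with a reference to WHO recommendations.
- Section 4.4: "Children treated with placebo will be treated at follow up (3-weeks post treatment) with 400 mg albendazole".
- Section 10.6, on the placebo arm that every cohort has: "this group will be treated with a standard treatment of 400 mg single dose albendazole at the end of the study (3-4 weeks later").

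Section 5.3 also says that infected people "excluded from the study due to one or several of the above-mentioned exclusion criteria, including withdrawals will be offered standard anthelminthic treatment (albendazole").

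**The concern.** The plan treats pregnancy as a reason not to give albendazole in the trial, and it checks for pregnancy before the randomized dose. The end-of-study dose is also written into the protocol and given by the study team, and 400 mg is itself one of the randomized doses. Yet no current check is tied to it. A woman who conceived after the baseline test, or whose pregnancy was too early to detect then, would be dosed if the plan were followed as written.

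The placebo arms show the gap most clearly. There the only described test precedes a placebo, and the first active dose comes weeks later with no test. A woman in an active arm who remains egg-positive faces the same question with a second dose.

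The offer in section 5.3 is a related gap. A woman found pregnant at screening is kept out of the trial but, on the wording, is then offered the same drug with no separate rule.

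**Working it through.** The plan states no figure on this point, so the check sets the provisions side by side and then works out the interval and the scale.

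**Test against dose.**

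| Event | Where | Pregnancy test or rule attached? |
|---|---|---|
| Randomized dose | 4.3.1, 5.3 | Yes: urine test, exclusion if pregnant |
| End-of-study dose, all still positive | 4.3.2 | None |
| End-of-study dose, all still positive | 10.2 | None named; WHO recommendations cited |
| End-of-study dose, placebo children | 4.4 | None |
| End-of-study dose, placebo arm of each cohort | 10.6 | None |
| Offer to excluded infected people | 5.3 | None; pregnancy is among the listed exclusions |

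The text on organ function shows that where the plan wants a baseline examination repeated, it says so. The pregnancy sentence beside it carries no repeat.

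**Interval between test and dose.** The test day is not stated. The test falls under the heading for clinical and biological examinations, and section 4.6 places the clinical examination and biochemistry at hour 0. Taking the test as day 0:

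- Earliest dose, at the start of the follow-up window (4.3.2): 14 − 0 = 14 days.
- Latest dose, at 4 weeks (10.6): 28 − 0 = 28 days.
- Placebo arms, at 3 to 4 weeks (4.4, 10.6): 21 to 28 days.

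**Scale in the placebo arms.** Inputs are 40 per arm and 5% loss (7.2), and one placebo arm in each of the two adult cohorts (10.6). Adults: 2 × 40 = 80, and 80 × 0.95 = 76 seen at follow-up, both sexes together. The documents give neither the share who are women, nor the share of those who could become pregnant, nor the number of girls above 10 in the 6–12 cohorts. The calculation stops there.

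**The case against.** The strongest case on the other side has four parts.

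1. *The dose is governed elsewhere.* Section 10.2 ties it to WHO recommendations, and 4.3.2 describes it as the current standard treatment, so handling of pregnancy may follow from that guidance. This weakens the point but does not remove it. The reference names no test, and sections 4.3.2, 4.4 and 10.6 do not repeat it.

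2. *Clinical discretion already exists.* Section 9.3 gives the physician responsibility for medical aspects and lets the investigator take protective steps beyond the protocol. That stands. But a physician can act on a pregnancy only if it is known, and no step is described that would reveal it.

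3. *The instruction may lie in material not seen.* The cohort flow charts, the consent pages and the drug package leaflet (Appendix 1) are not visible. This stands, and the point is limited to the visible text.

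4. *The documents do not state what harm a single 400 mg dose does in pregnancy.* Correct. The exclusion in 5.3 was written for randomized dosing of up to 800 mg. The point is therefore one of consistency: the plan's own check precedes one protocol dose and not the other.

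Two stronger readings are tempting and are not supported. A reader might infer a gap of up to 56 days, from a test on day −28 and a dose at 4 weeks (28 + 28). No visible text places the urine test at day −28, and the schedule points to day 0.

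A reader might also infer a number of women at risk. At the assumed cure rates, adults due the dose number 80 in the placebo arms, 40 × (0.70 + 0.50 + 0.30 + 0.20) = 68 in the hookworm active arms and 40 × (0.80 + 0.70 + 0.60) = 84 in the *T. trichiura* active arms. The total is 232, or about 220 of 360 after 5% loss. If 40–60% are women (an assumption), that is 88–132. The arithmetic is right, but it does not measure the risk. Adults have no upper age limit, the sex split is assumed, and women known to be pregnant at baseline are already excluded.

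**Conclusion.** The point holds for the visible text. The urine pregnancy test is described only at baseline, and the end-of-study albendazole dose has no test attached. On a day-0 test, the interval is about 2 to 4 weeks overall and 3 to 4 weeks in the placebo arms, whose first active trial dose this is. The offer in section 5.3, read literally, extends to people excluded because they are pregnant.

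The conclusion rests on two conditions: that the test is done on day 0, and that the material not shown contains no repeat-test instruction. The number of women of childbearing potential is unknown and no number of pregnancies can be estimated.

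A reader might also suspect an effect on the efficacy results. There is none, because the dose follows the endpoint assessment. This is a participant-safety gap that is cheap to close.

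**What to change.** 1. In section 4.3.1, add that the urine pregnancy test is repeated in females above 10 years at follow-up, immediately before the end-of-study albendazole dose. A participant who tests positive is not dosed at that visit and is referred to the study physician. Add a matching row to the schedule in 4.6, marked at baseline and at follow-up.
2. In section 5.3, state that people excluded because of pregnancy are referred to the study physician, who decides on treatment and its timing, and are not offered albendazole automatically.

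The cost is one urine test for each female above 10 years who is due the dose, at a visit that already collects stool and blood. The 5.3 change is wording only. For the placebo group, section 10.6 itself expects no harm from waiting 3 to 4 weeks for treatment, so a short deferral for physician review is consistent with the plan's own reasoning. Randomization, endpoints and analysis do not change.
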